#### 8.5. Management of Acute Reactions

#### 8.5.1. Systemic Injection Reactions

Emergency equipment and medication for the treatment of systemic reactions must be available for immediate use. All injection reactions must be reported as AEs (as defined in Section 10.2.1) and graded using the grading scales as instructed in Section 10.2.4.

Acute systemic reactions following SC injection of study drug should be treated using clinical judgment to determine the appropriate response according to typical clinical practice.

#### 8.6. Method of Treatment Assignment

Approximately 60 patients will be randomized at baseline/week 0/visit 2 in a 1:1 ratio to receive either dupilumab 300 mg Q2W or placebo according to a central randomization scheme provided by an interactive voice response system (IVRS)/interactive web response system (IWRS) to the designated study pharmacist (or qualified designee). Randomization will be stratified by region (pooled country), by chronic systemic corticosteroid use (yes/no) at screening, and by oral antifungal use (yes/no) at screening.

#### 8.7. Blinding

Study patients, the principal investigators, and study site personnel will remain blinded to all randomization assignments throughout the study. The Regeneron medical/study director, study monitor, and any other Regeneron and contract research organization (CRO) personnel who are in regular contact with the study site will remain blinded to all patient randomization assignments.

Blinded study drug kits coded with a medication numbering system will be used. In order to maintain the blind, lists linking these codes with product lot numbers will not be accessible to individuals involved in study conduct.

Anti-drug antibody, drug concentration results, and post-treatment biomarker results (**Mathematical Science**, serum total IgE, and *A fumigatus*-specific IgEs) will not be communicated to the sites, and

the sponsor's operational team will not have access to results associated with patient identification until after the database is locked for the respective study part.

#### 8.8. Emergency Unblinding

Unblinding of treatment assignment for a patient may be necessary due to a medical emergency or any other significant medical event (eg, pregnancy) and when a treatment decision is contingent on knowing the patient's treatment assignment. Study drug will be discontinued for patients whose treatment has been unblinded/unmasked (Section 8.4.2).

- If unblinding is required:
  - Only the investigator will make the decision to unblind the treatment assignment.
  - Only the affected patients will be unblinded.
  - The designated study pharmacist(s)/designee at the study site will provide the treatment assignment to the investigator. If there is no study pharmacist, the investigator for the site will unblind/unmask the patient. Unblinding is performed using the IVRS/IWRS which will notify Regeneron.
  - The investigator will notify Regeneron and/or designee as soon as possible after unblinding the patient.

Treatment assignment is not to be provided to site personnel, other than the unblinded study pharmacist (when applicable), at any time during the conduct of the study, except in the case of a true emergency and when a treatment decision is contingent on knowing the patient's treatment assignment. In the event that there is no study pharmacist, the individual at the site fulfilling that role will be the only unblinded member of the site personnel.

#### 8.9. Treatment Logistics and Accountability

#### 8.9.1. Packaging, Labeling, and Storage

A medication numbering system will be used to label blinded investigational study drug. Lists linking medication numbers with product lot numbers will be maintained by the groups (or companies) responsible for study drug packaging. In order to maintain the blind, these lists will not be accessible to individuals involved in study conduct.

Study drug will be stored at the site at a temperature of 2°C to 8°C; storage instructions will be provided in the pharmacy manual.

#### 8.9.2. Supply and Disposition of Treatments

Study drug will be shipped at a temperature of 2°C to 8°C to the investigator or designee at regular intervals or as needed during the study. At specified time points during the study (eg, interim site monitoring visits), at the site close-out visit, and following drug reconciliation and documentation by the site monitor, all opened and unopened study drug will be destroyed or returned to the sponsor or designee.

#### 8.9.3. Treatment Accountability

All drug accountability records must be kept current.

The investigator must be able to account for all opened and unopened study drug. These records should contain the dates, quantity, and study medication

- dispensed to each patient
- returned from each patient (if applicable), and
- disposed of at the site or returned to the sponsor or designee.

All accountability records must be made available for inspection by the sponsor and regulatory agency inspectors; photocopies must be provided to the sponsor at the conclusion of the study.

#### 8.9.4. Treatment Compliance

All drug compliance records must be kept current and made available for inspection by the sponsor and regulatory agency inspectors.

#### 8.10. Concomitant Medications and Procedures

Any treatment administered from the time of informed consent to the final study visit will be considered concomitant medication. This includes medications that were started before the study and are ongoing during the study.

#### 8.10.1. Prohibited Medications and Procedures

Treatment with the following concomitant medications is prohibited during the study:

- Systemic immunosuppressive/immunomodulating drugs (including, but not limited to: omalizumab, cyclosporine, mycophenolate-mofetil, azathioprine, methotrexate, IFN-γ, or other biologics) other than protocol-defined use of corticosteroids
- Treatment with an investigational drug (other than dupilumab)
- Initiation of SCIT, or change in dose for those patients on a stable dose of SCIT within 1 year prior to screening
- SLIT
- Oral immunotherapy
- Treatment with a live (attenuated) vaccine:
  - Chickenpox (varicella)
  - FluMist-influenza
  - Intranasal influenza
  - Measles (rubeola)
  - Measles-mumps-rubella combination
  - Measles-mumps-rubella-varicella combination

- Mumps
- Oral polio (Sabin)
- Oral typhoid
- Rubella
- Smallpox (vaccinia)
- Yellow fever
- Bacille Calmette-Guerin
- Rotavirus
- Varicella zoster (shingles)
- The following concomitant procedures are prohibited during the study period:
  - Major elective surgical procedures
  - Bronchial thermoplasty

#### 8.10.2. Permitted Medications

Other than the prohibited medications listed in Section 8.10.1, treatment with concomitant medications are permitted during the study. This includes topical and systemic anti-infective medications for any duration, use of contraceptives, nasal and inhaled corticosteroids, and oral antihistamines for any duration. Antifungal therapy to treat ABPA is described in Section 8.2.

Medications used to treat chronic diseases such as diabetes, hypertension, and asthma (ICS plus 1 or more additional controller medications [eg, LABA, LTRA, LAMA, etc], and/or systemic steroids [see Section 8.2]) are permitted during the study. If there is any question regarding whether a concomitant medication may be used during the study, the study site should contact the medical monitor.

## 9. STUDY SCHEDULE OF EVENTS AND PROCEDURES

#### 9.1. Schedule of Events

In light of the public health emergency related to COVID-19, the continuity of clinical study conduct and oversight may require implementation of temporary or alternative mechanisms. Examples of such mechanisms may include, but are not limited to, any of the following: phone contact, virtual visits, telemedicine visits, online meetings, non-invasive remote monitoring devices, use of local clinic or laboratory locations, and home visits by skilled staff. Additionally, no waivers to deviate from protocol enrollment criteria due to COVID-19 will be granted. All temporary mechanisms utilized, and deviations from planned study procedures are to be documented as being related to COVID-19 and will remain in effect only for the duration of the public health emergency.

Study assessments and procedures are presented by study period and visit in Table 1.

#### Table 1:Schedule of Events

												Ran	domi	zed tr	eatm	ent pe	eriod*	*												
Study Procedure	Screening Visit a	Randomization/ Baseline Visit b																										EOT visit	EOS visit	Unscheduled Visit z
											Р	hone visit	call s			Pho	ne cal	l visits	3		Pl	hone o visits	call S		Р	hone visit	call s			
Week	-4	0	2	4	6	8	10	12	14	16	18	20	22	24	26	28	30	32	34	36	38	40	42	44	46	48	50	24- 52**	36- 64	
Visit	1	2 c	3	4	5*	6	7*	8	9*	10*	11	12	13	14	15	16	17	18	19	20	21	22	23	24	25	26	27	14- 28	15- 29	
Window (days)	±7	±3	±3	±3	±3	±3	±3	±3	±3	±3	±3	±3	±3	±3	±3	±3	±3	±3	±3	±3	±3	±3	±3	±3	±3	±3	±3	±3	±7	
Screening/Baselin	ie:																													
Inclusion/ Exclusion	Х	Х																												
Informed Consent/Assent	Х																													
Medical and surgical history	х																													
Demographics	Х																													
Pre- and post- bronchodilator spirometry d,e	Х																													
Qualifying ACQ-5	х																													
ANCA, Hepatitis and HIV serology f	х																													
Tuberculosis testing g	Х																													
Serum pregnancy test h,i	Х																													
A fumigatus skin testing	Х																													
Serum IgG and precipitins against A fumigatus	х																													

**REGENERON CONFIDENTIAL** 

Page 56 of 99

												Ran	domiz	zed tr	eatm	ent pe	riod*	*												
Study Procedure	Screening Visit a	Randomization/ Baseline Visit b																										EOT visit	EOS visit	Unscheduled Visit z
											P	hone visit	call s			Phor	ne call	visits	3		P	hone c visits	all		Р	hone visit	call s			
Week	-4	0	2	4	6	8	10	12	14	16	18	20	22	24	26	28	30	32	34	36	38	40	42	44	46	48	50	24- 52**	36- 64	
Visit	1	2 c	3	4	5*	6	7*	8	9*	10*	11	12	13	14	15	16	17	18	19	20	21	22	23	24	25	26	27	14- 28	15- 29	
Window (days)	±7	±3	±3	±3	±3	±3	±3	±3	±3	±3	±3	±3	±3	±3	±3	±3	±3	±3	±3	±3	±3	±3	±3	±3	±3	±3	±3	±3	±7	
						!				!																				
Urine toxicology	Х																													
Smoking history	Х																													
Prior & concomitant medications	Х	Х	Х	X	Х	X	X	Х	Х	Х	Х	Х	Х	Х	Х	Х	Х	Х	Х	Х	Х	Х	Х	Х	Х	Х	Х	Х	Х	Х
Randomization		X																										ш		
Treatment:					Tra			N.	X7.4	× 7.4				N/																
Call IVRS/IWRS K	Х	Х	Х	X	X*	X	X*	Х	Х*	Х*				Х						Х				Х				X	X	
drug 		Х	Х	X	X	X	X	Х	Х	Х	Х	Х	Х	Х	Х	Х	Х	Х	Х	Х	Х	Х	Х	Х	Х	Х	X			
Dispense /Review home dosing paper diary	х	x	Х	х	X*	х	X*	х	X*	X*				X						X				Х				х		Х
OCS dose titration for pts on OCS at baseline				x	X*	x	X*	х	X*	X*																				
Efficacy:																														
Spirometry d		X	Χ	X	X*	X	X*	Х	Х*	X*				Х						Х				Χ				Χ	Χ	
Post-BD spirometry d		Х	Х	Х				Х						Х						Х								Х		L
ACQ-5 score m		Х	Х	Х	X*	Х	X*	Х	Х*	X*				Х						Х				Х				Х	Х	_
SGRQ Score m		Х		Х				Х						Х						Х								Х	Х	

**REGENERON CONFIDENTIAL** 

		Randomized treatment period**																												
Study Procedure	Screening Visit a	Randomization/ Baseline Visit b																										EOT visit	EOS visit	Unscheduled Visit 
											P	hone visit	call s			Phor	ne cal	l visits			P	hone c visits	all		P	hone o visits	call S			
Week	-4	0	2	4	6	8	10	12	14	16	18	20	22	24	26	28	30	32	34	36	38	40	42	44	46	48	50	24- 52**	36- 64	
Visit	1	2 c	3	4	5*	6	7*	8	9*	10*	11	12	13	14	15	16	17	18	19	20	21	22	23	24	25	26	27	14- 28	15- 29	
Window (days)	±7	±3	±3	±3	±3	±3	±3	±3	±3	±3	±3	±3	±3	±3	±3	±3	±3	±3	±3	±3	±3	±3	±3	±3	±3	±3	±3	±3	±7	
Safety:																														
Vital Signs n	Х	Х	Х	Х	X*	Х	X*	Х	X*	X*				Х						Х				Х				Х	Х	Х
Physical examination o	х	х		х				Х						Х						Х								х	х	Х
Electro-cardiogram p	Х																											Х		
Adverse Events	Х	Х	Х	Х	Х	Х	Х	Х	Х	Х	Х	Х	Х	Х	Х	Х	Х	Х	Х	Х	Х	Х	Х	Х	Х	Х	Х	Х	Х	Х
Laboratory Testi	ng:																													
Hematologyq	Х	Х		Х		Х		Х						Х						Х				Х				Х	Х	Х
Blood chemistry r	Х	Х		Х				Х						Х						Х								Х	Х	
Urinalysis s	Х	Х												Х														Х	Х	
Urine pregnancy test t		х		Х		Х		Х						Х						Х				Х				х	х	
Pharmacokinetics	s and	ADA	Sam	ıplin	g																									
Drug concentration sample u		x						Х						X														х	Х	
ADA sample u		Х						Х						Х														Х	Х	
Biomarkers:																														
FeNO v	Х	Х		Х		Х		Х						Х						Х				Х				Х	Х	
Serum total IgE w	Xe	Х		Х		Х		Х						Х						Х								Х	Х	Х
Serum A fumigatus specific IgE	Xe	X		X				Х						Х						Х								Х	Х	

**REGENERON CONFIDENTIAL** 

Page 58 of 99

			Randomized treatment period**																											
Study Procedure	Screening Visit a	Randomization/ Baseline Visit b																										EOT visit	EOS visit	Unscheduled Visit z
											P	hone ovisit	call s			Phor	ne call	l visits	5		P	hone c visits	all		Р	hone visit	call s			
Week	-4	0	2	4	6	8	10	12	14	16	18	20	22	24	26	28	30	32	34	36	38	40	42	44	46	48	50	24- 52**	36- 64	
Visit	1	2 c	3	4	5*	6	7*	8	9*	10*	11	12	13	14	15	16	17	18	19	20	21	22	23	24	25	26	27	14- 28	15- 29	
Window (days)	±7	±3	±3	±3	±3	±3	±3	±3	±3	±3	±3	±3	±3	±3	±3	±3	±3	±3	±3	±3	±3	±3	±3	±3	±3	±3	±3	±3	±7	
Pharmacogenomi	cs an	d futi	ure b	iome	edica	ıl res	searc	:h:																						
Blood samples for future Biomedical research		х		х				х						Х						x				Х				X		
Whole blood RNA x (optional)		x																												
Whole blood for DNA x (optional)		х																												
Blood immunophenotyping substudy y (optional)		х		х				x																				Х		

NOTE: EOS is end of study; the follow-up period begins at the EOT visit and ends at the EOS visit.

#### 9.1.1. Footnotes for the Schedule of Events Table

#### Footnotes for Table 1 Schedule of Events

\*Visits 5, 7, 9, and 10 will be performed as phone visits for patients not receiving OCS at baseline. For patients receiving OCS at baseline, these visits should be performed in-clinic if the patient remains on OCS on the day of the clinic visit. If OCS has been discontinued, these visits can be either in-clinic or performed as a phone visit at the discretion of the investigator. Assessments/procedures marked with an asterisk should only be performed if the visit occurs in-clinic.

\*\*After the last patient has completed visit 14/week 24 of the treatment period or withdrawn from the study, all patients still currently in the treatment period (between visit 15/week 26 and visit 27/week 50) should return to the clinic 2 weeks from their last dose/treatment administration to complete their EOT visit and all its applicable assessments. For patients who have withdrawn from the study treatment but remain in the study, the EOT visit will take place 2 weeks from their last visit. All patients must have their EOS visit 12 weeks after their EOT visit.

- a. Prior to screening, patients must be on a stable background therapy for asthma which may include ICS in combination with a second controller medication (eg, LABA, LTRA, theophylline, etc) for at least 3 months with a stable dose ≥1 month prior to baseline. Patients requiring a third controller are allowed to participate in this study. The third controller should also be used for at least 3 months with a stable dose ≥1 month prior to visit 1. Patients requiring systemic steroids of up to 10 mg per day (or up to 30 mg every alternate day) as controller medication are permitted.
- b. Randomization/baseline visit is defined as day 1. The visit schedule should be adhered to within  $\pm 1$  week for the screening period,  $\pm 3$  days for the randomized IMP treatment period, and  $\pm 7$  days for the post-IMP treatment period.
- c. All assessments at visit 2 (day 1) are to be conducted pre-IMP dose except for the assessment of local tolerability of SC injections.
- d. Spirometry will be done locally according to European Respiratory Society (ERS)/American Thoracic Society (ATS) guidance, but measured by a central laboratory. Spirometry will be performed during a trough period of bronchodilators according to their action duration, for example, withholding the last dose of salbutamol/albuterol or levosalbutamol/levalbuterol for at least 6 hours, withholding the last dose of ipratropium for at least 8 hours, withholding the last dose of LABA for at least 12 hours (ultra-long-acting LABA-like vilanterol should be withheld for at least 24 hours), and withholding the last dose of LABA for at least 0 before performing the measurements. Post-bronchodilator FEV1 will be determined at the designated treatment visits.
- e. Three attempts may be made during the screening period until the baseline visit to meet the qualifying criteria for FEV1. A total of 2 attempts may be made during the screening period until the baseline visit to meet the qualifying criteria for blood eosinophils, total serum IgE, *Aspergillus*-specific IgE, *Aspergillus*-specific IgG, *Aspergillus* precipitins, and/or skin prick test.

- f. Clinical laboratory testing at screening visit 1 will include hepatitis screen covering HBsAg, HBsAb, HBcAb), hepatitis C virus antibodies, HIV screen (anti-HIV-1 and anti-HIV-2 antibodies). In case of results showing HBsAg (negative), and HBcAb (positive), an HBV DNA testing will be performed prior to randomization to rule out a false positivity if the investigator believes the result is a false positive, or to clarify the serological status if the investigator finds it unclear to interpret in absence of known HBV infection. In case of results showing HCV Ab (positive), an HCV RNA testing may be performed to rule out a false positivity, if the investigator believes the patient is a false positive.
- g. Patients with active tuberculosis or non-tuberculous mycobacterial infection, latent untreated tuberculosis, or a history of incompletely treated tuberculosis will be excluded from the study unless it is well documented by a specialist that the patient has been adequately treated, and can now start treatment with a biologic agent in the medical judgment of the investigator and/or infectious disease specialist. (Tuberculosis testing will be performed on a country-by-country basis according to local guidelines if required by regulatory authorities or ethics committees [ECs].)
- h. Only for women of childbearing potential. Pregnancy will lead to definitive treatment discontinuation in all cases. In case of positive urinary test, a serum pregnancy test should be performed as soon as possible to confirm the pregnancy.
- i. Serum pregnancy test will be conducted at visit 1 and urine dipstick pregnancy tests will be conducted at other visits. A negative result must be obtained at visits 1 and 2 prior to randomization.

- k. IVRS/IWRS will be utilized during screening to assign screening IDs, during baseline to provide treatment assignments to the investigator, and to dispense study drug.
- Every 2 weeks, study drug administrations must be separated by at least 11 days. IMP can be administered in clinic at scheduled visits or at home (patient, caregiver, or health care professional). Patients and parents/caregivers who prefer to have clinic staff administer study drug may choose to have injections administered in the clinic. Due to the COVID-19 pandemic, study drug may be shipped from the clinical site to the patient's home if necessary.
- m. ACQ-5 and SGRQ are completed in the electronic diary during clinic visits and prior to spirometry at each visit. NOTE: If COVID-19 restrictions limit the availability of staff or the patient to have in-clinic visits, site staff should make every effort to conduct telephone interviews to complete these questionnaires. Site staff should conduct the telephone interviews on the date of scheduled site visit by following an interview guide provided by the sponsor. Patient responses from the interviewer administered questionnaires will be captured by the site staff.
- n. Vital signs, including systolic and diastolic blood pressure (mmHg), pulse rate (beats per minute), body temperature (°C), and respiratory rate will be measured at screening, baseline, and every subsequent on-site visit. For adults, height (cm) will be measured only

REGENERON CONFIDENTIAL Page 61 of 99

at screening (visit 1), and body weight (kg) will be measured at screening (visit 1) and at EOT/EOS visits. For adolescents, height and body weight will be measured at the screening and randomization visits (visits 1 and 2) and every subsequent visit.

- o. Complete physical examinations will include skin, nasal cavities, eyes, ears, and respiratory, cardiovascular, gastrointestinal, neurological, lymphatic, and musculoskeletal systems.
- p. 12-lead ECG is to be read centrally.
- q. Hematology will include hemoglobin, hematocrit, platelet count, total white blood cell (WBC) count, differential count, and total red blood cell (RBC) count.
- r. Hematology will include hemoglobin, hematocrit, platelet count, total white blood cell count, differential count, and total red blood cell count.
- s. Urinalysis will include specific gravity, pH, glucose, ketones, blood, protein, nitrate, leukocyte esterase, urobilinogen, and bilirubin. If any parameter on the dipstick is abnormal, a urine sample should be sent to the central laboratory for quantitative measurement. If positive for protein and/or red blood cells, microscopic analysis will be performed by the central laboratory.
- t. Serum pregnancy test will be conducted at visit 1 and urine dipstick pregnancy tests will be conducted at other visits. A negative result must be obtained at visits 1 and 2 prior to randomization.
- u. Pharmacokinetic (PK) and ADA samples are to be collected prior to the administration of the drug. In the event of suspected serious adverse events (SAEs), such as anaphylaxis or hypersensitivity, additional samples for the analysis of ADA and dupilumab drug concentration may be collected as close to the event as practically possible.
- v. Exhaled nitric oxide assessment is conducted prior to spirometry and following a fast of  $\geq 1$  hour.
- w. If the patient experiences an exacerbation, an unscheduled visit is to be performed for the collection of an additional blood sample for serum total IgE at the time of, or as soon as possible after, the exacerbation.
- x. If collection is not completed at randomization, sample can be taken at a following visit. To be collected prior to IMP administration
- y. Blood samples will be collected at selected sites. Only patients who are not on chronic systemic corticosteroids and not on oral antifungal therapy at baseline will be allowed to participate in the blood immunophenotyping substudy.
- z. Unscheduled visits may be necessary to repeat testing following abnormal laboratory results, for follow-up of AEs, or for any other reason as warranted. If the patient develops a respiratory exacerbation, he/she will be required to have an unscheduled visit as soon as possible, and a blood sample for serum total IgE needs to be collected.

#### 9.1.2. Early Termination Visit

Patients who are withdrawn from the study will be asked to return to the clinic once at the time of the next regularly scheduled visit for an early termination visit consisting of the end of study assessments described in Table 1.

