#### Patients on Chronic Oral Corticosteroids at Baseline:

REGENERON CONFIDENTIAL

Page 36 of 99

Patients who experience a severe respiratory exacerbation will have, as soon as possible, an unscheduled visit at the site for the collection of a blood sample for serum total IgE measurement.

Patients who withdraw from the study prematurely will have, at the time of their next regularly scheduled visit, an early termination visit. This early termination visit will consist of all assessments normally planned for the end of study (EOS) visit. To allow assessment of patient outcomes over the stipulated study period, patients who discontinue study treatment but continue in the study will be asked and encouraged to complete all remaining study visits and participate in all safety follow-up assessments according to the visit schedule (Table 1).

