10.4. Electrocardiography

The following standard 12-lead electrocardiography (ECG) parameters will be recorded and summarized by treatment group according to the Schedule of Time and Events in Section 14.2:

- Mean heart rate
- P wave, R wave (PR) interval
- Q wave, R wave, S wave (QRS) duration
- Q wave, T wave (QT) interval
- QT interval corrected for heart rate using Bazett's formula (QTcB), where QTcB (ms) = QT/\sqrt{RR} , QT is the uncorrected QT interval measured in ms, and RR (the elapsed time between 2 successive R waves) is 60/HR with HR being the heart rate in beats per minute.
- QT interval corrected for heart rate using Fridericia's formula (QTcF), where QTcF (ms) = $QT/RR^{1/3}$, QT is the uncorrected QT interval measured in ms, and RR (the elapsed time between 2 successive R waves) is 60/HR with HR being the heart rate in beats per minute.
- RR interval
- Interpretation, i.e., overall ECG status along with findings.

ECG measurements and change from baseline at all scheduled post-baseline assessment time points will be summarized via descriptive statistics by treatment group.

ECG parameters will be evaluated by PCSV criteria, specifically identifying patients with at least 1 post-baseline measurement that meets the PCSV criteria (see Section 14.3). Patients meeting the PCSV criteria will be summarized by patient count (and percentage) for a post-baseline PCSV measurement by treatment group.

Shift tables will be constructed showing patients' transition in ECG status from baseline to specified post-baseline time points by treatment group. ECG status will be categorized as Normal, Abnormal (Not Clinically Significant), or Abnormal (Clinically Significant).

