11.3. Data for Non-Efficacy Endpoints

Date of First/Last Study Drug Injection

The date of first study drug injection (equivalently, the date of first dose of study drug administered) is the earliest date of study drug injection among the non-missing, non-zero dosing records documented in the Study Drug Administration eCRF.

The date of last study drug injection (equivalently, the date of the last dose of study drug administered) is the latest date of study drug injection among the non-missing, non-zero dosing records documented in the Study Drug Administration eCRF. If a patient's date of last dose is missing or unknown, his/her last visit date (including phone call visits) up to but not including the EOT visit will be substituted.

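### Patients who withdraw from the study before the end-of-treatment visit have no scheduled post-baseline ECG and no scheduled home-dosing diary review at exit

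*Protocol*

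**What the plan says.** Protocol 9.1.2 brings a withdrawing patient back once, at the next regularly scheduled visit, "for an early termination visit consisting of the end of study assessments described in Table 1". Protocol 6.1 has the same rule: "This early termination visit will consist of all assessments normally planned for the end of study (EOS) visit". SAP 2.1 repeats it.

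In Table 1 the row "Electro-cardiogram" is marked at screening and EOT only. The row "Dispense /Review home dosing paper diary" is marked at EOT and at unscheduled visits but not at EOS. Home administration is allowed: "IMP can be administered in clinic at scheduled visits or at home" (Table 1 footnotes).

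SAP 5.2 identifies discontinuation from the study during the treatment period by an early termination visit with no EOT visit in the database. SAP 10.4 summarizes ECG change from baseline and status shifts, and evaluates PCSVs by "specifically identifying patients with at least 1 post-baseline measurement that meets the PCSV criteria".

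Under SAP 11.3 the last injection date "is the latest date of study drug injection among the non-missing, non-zero dosing records documented in the Study Drug Administration eCRF". That date sets exposure duration (SAP 9.1) and the end of the on-treatment period, which is last dose plus 14 days (SAP 10).

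**The concern.** The EOS column is written for a patient who finished treatment and then completed the 12-week follow-up. By then the EOT visit has already supplied the ECG and closed out the dosing diary. A patient who withdraws during treatment skips EOT, so the exit visit omits two items the plan intended to collect once, at the end of dosing.

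For the ECG, early leavers have nothing scheduled after screening. They are unlikely to be a random subset, since some will leave because of an adverse event, and the tables would describe mainly those who stayed.

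For dosing, the last injections may have been given at home since the last clinic review. Their dates feed exposure, compliance and the on-treatment window that SAP 10 uses to support the secondary endpoint on treatment-emergent adverse events through end of treatment.

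**Working it through.** The plan states no figure to reproduce here. The check is a column reading of Protocol Table 1 plus some day counting. Table 1 has 30 visit columns: screening, Weeks 0 to 50 every two weeks (26 columns), EOT, EOS and unscheduled (1 + 26 + 3 = 30). The copy in SAP 14.2 is broken in the extracted text, so I rely on the Protocol table.

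| Row | Where marked | EOT | EOS | Unscheduled |
|---|---|---|---|---|
| 12-lead ECG | Screening, EOT | yes | no | no |
| Home-dosing diary | Screening, Weeks 0, 2, 4, 6\*, 8, 10\*, 12, 14\*, 16\*, 24, 36, 44, EOT, unscheduled | yes | no | yes |
| Post-bronchodilator spirometry | Weeks 0, 2, 4, 12, 24, 36, EOT | yes | no | no |
| Vital signs | Every in-clinic visit | yes | yes | yes |
| Urinalysis | Screening, Weeks 0, 24, EOT, EOS | yes | yes | no |

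\* Only if the visit is in clinic; these are phone visits for patients not on oral corticosteroids (OCS) at baseline.

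**ECG.** A patient who reaches EOT has 2 scheduled ECGs, screening and EOT. A patient who withdraws before EOT has 1, so 0 after baseline. With the dropout rate redacted, I assume 5% to 20%: 0.05 × 60 = 3 and 0.20 × 60 = 12 patients.

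**Doses between diary reviews.** For a patient not on OCS at baseline, in-clinic reviews from Week 12 on fall at Weeks 12, 24, 36, 44 and EOT. If the exit visit replaces Week 24, the doses with no scheduled review are Weeks 14, 16, 18, 20 and 22, which is 5. Replacing Week 36 also gives 5 (Weeks 26 to 34). Replacing Week 44, or an EOT at Week 52, gives 3.

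**Effect on the on-treatment window, worst case.** The target day is 7 × week + 1. Week 12 is Day 85, Week 22 is Day 155 and Week 24 is Day 169. Suppose all five doses were given but none reached the eCRF:

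- Recorded last dose Day 85: window closes on Day 85 + 14 = 99.
- True last dose Day 155: window closes on Day 155 + 14 = 169.
- Adverse events starting on Days 100 to 169 would move from on-treatment to follow-up.
- With the recorded date, follow-up starts at Day 85 + 15 = 100 and runs 84 days, to about Day 184. Those events stay inside the treatment-emergent period.

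**Fallback.** If the last-dose date is missing or unknown, SAP 11.3 substitutes the last visit date, phone visits included, up to but not including EOT. Here that is Day 155 (the Week 22 call), giving the correct Day 169. If the exit visit itself on Day 169 counts as the last visit, the window closes on Day 183. Either way it does not close early. If five doses are simply absent and no date is flagged as unknown, the rule takes the latest recorded date and the fallback is not triggered.

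**The case against.** A reader might infer that the last home doses of early leavers go unreconciled. The documents do not support that. Protocol 8.9.3 requires the investigator to account for all opened and unopened drug, with dates and quantities dispensed to and returned from each patient. Section 8.9.2 has the monitor document reconciliation. Study drug administration is marked every two weeks through Week 50, phone visits included, and nothing makes the paper diary the only source for the eCRF. Five consecutive unrecorded doses would also look like a breach of the limit on missed doses in Protocol 8.4.2.2 and would probably be queried. The Day 85 case therefore needs several safeguards to fail together. What remains is narrow: accountability does not expressly require the date of each home injection, and the fallback needs a date that is recognized as missing.

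On the ECG, patients who stop drug are encouraged to remain in the study and then have an EOT visit (Protocol 8.4.2, 9.1.4), so the gap concerns only those who leave altogether. An ECG can be obtained at an unscheduled visit if warranted. No listed adverse event of special interest is cardiac, and the EOS column still supplies vital signs, physical examination, laboratory tests, drug concentration and ADA. All of this stands and limits the importance of the gap. It does not put a scheduled post-baseline ECG into the plan for these patients.

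Post-bronchodilator spirometry is also missing from the EOS column, but I attach no consequence to it: pre-bronchodilator spirometry, which carries the primary endpoint, is there.

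**Conclusion.** The ECG point holds. Followed as written, the plan schedules no post-baseline ECG for anyone who withdraws from the study before EOT, and the SAP 10.4 tables rest on patients who reached EOT plus any ad hoc recordings. The range of 3 to 12 patients is only as good as the assumed 5% to 20% withdrawal rate.

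The diary point holds only as the absence of a scheduled check on the dates of the last home injections. The 70-day shift in the window (169 − 99) is an upper bound and unlikely.

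Two further readings are tempting but wrong. Adverse events are not lost: any that are reclassified leave the on-treatment tables and stay in the overall treatment-emergent ones (SAP 10). The primary analysis is not affected either. This is a modest gap in safety data collection, worth closing because closing it is cheap.

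**What to change.** In Protocol 6.1 and 9.1.2 and in SAP 2.1, state that a patient who withdraws during the treatment period has, at the early termination visit, the EOS assessments plus the two EOT-only items: the ECG and the home-dosing diary review. The EOS column alone can stay for withdrawals during follow-up.

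Record the visit as early termination, not EOT. SAP 5.2 treats anyone with an EOT visit as having completed the treatment period, and SAP 11.4 codes every EOT visit as Week 52, so an exit visit entered as EOT would turn a withdrawal into a Week 52 completer.

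State in the SAP that this ECG counts as a post-baseline value in the PCSV and shift summaries. The visit-window rules in SAP 11.4 do not clearly place an exit ECG taken well before Week 52.

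The cost is a sentence in each of three sections, a line on the ECG summaries and a slightly longer exit visit. Both items were already planned once per patient at EOT. Patients who attend no exit visit will still not be captured.
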